For the primary objective of the study, improved cosmesis will be analyzed using data from the POSAS, as a total score, and separately for the observer score and then the subject score. Changes from baseline will be examined at 3 months, 6 months and again at 1 year post treatment. TEWL will be considered at 3 months, 6 months, and 1 year. This analysis may also consider the baseline status of the burn including depth, surface area, location of the burn injury and subject baseline characteristics (age, concomitant injury).

Protocol version: 5

Template updated 5 Jul 2021

Secondary objectives include determining whether KeraStat Gel wound dressing results in less painful dressing changes, faster reepithelialization, and reduction in need for excision and grafting. Improvement in pain will be assessed using the scoring from the VAS pain scale at Screening, Days 7, 14, 21 and 28. Box plots of the VAS pain scores will be presented displaying the medians and quartiles in each treatment group over time. A nonparametric test will be used to determine changes in the score across time (Kruskal-Wallis) as well. Reductions in excision and grafting will be analyzed by treatment groups using the same methods as the VAS pain score. Median time to 100% reepithelialization by study treatment group will be conducted, mean times (days) will be analyzed using a Wilcoxon test by treatment groups, as well as a time to event analysis for 90% or higher reepithelialization from baseline.

The incidence of adverse events will be reported and summarized by treatment group. Adverse events will be coded in MedDRA by system organ class and preferred terms (PT).

Human Subjects Protection

Subject Recruitment Methods

Subjects who present at the Burn Center at WF or UMC with qualifying burns as determined by the Investigator will be approached for inclusion in the study by study personnel.

Remuneration

Enrolled study subjects will be provided with one \$45 gas card per visit for office visits on days 14 and 28 and months 3, 6, and 12.

Informed Consent

All subjects must give their informed consent in accordance with the informed consent regulations in Title 21 CFR, Part 50. Each subject over 18 years and subjects under 18 and their legally authorized representative will execute written informed consent (and assent if applicable) before any study procedures are conducted. Study personnel will obtain written informed consent in the clinic.

Confidentiality and Privacy

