The Research Monitor, [name], III, MD FACS is responsible to oversee the safety of the research and report observations/findings to the IRB or a designated institutional official. The Research Monitor will review all unanticipated problems involving risks to subjects or others associated with the protocol and provide an independent report of the event to the IRB. The Research Monitor may discuss the research protocol with the investigators; shall have authority to stop a research protocol in progress, remove individual human subjects from a research protocol, and take whatever steps are necessary to protect the safety and well-being of human subjects until the IRB can assess the monitor’s report; and shall have the responsibility to promptly report their observations and findings to the IRB or other designated official.

Risks and Benefits

There are no known risks associated with using KeraStat Gel. ISO 10993 testing supports the safety of the product. ISO 10993-10 testing suggested that some subjects may experience irritation; however, a GLP preclinical study and a human repeat patch test indicate the product is a non-irritant. A human skin prick test found that the product does not elicit an allergic response. The currently known risks associated with participation in this study include: discomfort at the wound site, infection at the wound site, lack of wound closure, and an allergic reaction to the dressings, sedatives, narcotics, or any other drugs which might be administered concomitantly with the procedure. All subjects will be given information on potential side effects and will be offered the option of alternative treatments by the Investigator prior to enrolling in the study. There may also be other side effects that we cannot predict or are not known. Taking part in this research study may involve providing information that subjects consider confidential or private. Efforts, such as coding research records, keeping research records secure, and allowing only

authorized people to have access to research records, will be made to keep subject information safe.

Alternative treatments include but are not limited to other topical (applied to the skin) dressings, such as silver sulfadiazine or triple antibiotic ointment or saline-soaked gauze.

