Subjects will receive the study dressings (i.e., KeraStat Gel and KeraStat Gel-related secondary dressings) at no cost during the study. Based on initial performance testing in animals, burn wounds randomized to receive KeraStat Gel treatment may benefit from improved cosmesis, improved healing rates, reduced fibrosis and contraction, and no increase in infection rates compared to Mepilex Ag. Subjects will also be seen in the clinic regularly for visits and may gain more information about management of their condition. We hope the information learned from this study will benefit burn patients and clinicians in the future.

Subject Benefit to Participation in the Study

There are no identifiable direct benefits to participating in this study. However, there are some *potential* benefits to participation. Given that the burns will be examined more often than what is many times the typical approach, there is a potentially reduced risk of infection. Additionally, there is the potential for more rapid healing of the study burns treated with KeraStat.

Reporting of Unanticipated Problems, Adverse Events or Deviations

Any unanticipated problems, serious and unexpected AEs, deviations, or protocol changes will be promptly reported by the Principal Investigator or designated member of the research team to the Institutional Review Board (IRB) and Sponsor or appropriate government agency if appropriate.

An AE is defined as any unfavorable or unintended change in body structure, body function, laboratory result (e.g., chemistry, ECG), or worsening of a pre-existing condition associated temporally with the use of the test product, whether or not considered related to the test product. All AE will be recorded in the Case Report Form (CRF), and a cumulative total will be evaluated for each subject and across all subjects treated. AE and concomitant medications will be reported based on the MedDRA dictionary and evaluated for relationship to KeraStat Gel or dressing-related procedures. Any AE not requiring intervention will be reported at the discretion of the Investigator. AE, concomitant medications, and vital signs will be monitored and recorded at each study visit. Concomitant procedures will be assessed.

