AEs that are anticipated for this subject population include: neurological/psychological, cardiovascular, pulmonary, gastrointestinal, genitourinary, renal, musculoskeletal, blood, endocrine, skin/wound, infectious, eye/ear/nose/throat, chemical, and hematological complications.

While these events may be temporally associated with study participation, they are consistent with severe burns and may not be considered related to the study under most circumstances. An Investigator (to include other qualified study staff) will be responsible for evaluating individual

subjects and determining whether a specific event is potentially study-related or whether the event could be reasonably anticipated as normal sequelae of the subject's clinical status, injury, and hospital course.

In the event of an AE, the Investigator will use accepted institutional SOC guidelines (medical or surgical), as needed. Expected or unexpected AE will be managed according to institutional SOC guidelines.

All subjects will be treated to alleviate signs and symptoms as appropriate medical intervention dictates. All procedures or medical therapies related to treatment of the complication will be recorded. Investigator assessment of reasons for failure and medical/surgical management will be recorded in the CRF. Subjects who are discontinued from study treatment will remain in the study for safety assessments and efficacy analysis.

All AE will be recorded on the CRF. The time of the onset, location, duration, intensity, relationship to the test product, treatment, and follow-up will also be captured on the CRF. The relationship between the application of KeraStat Gel and the AE will be determined by the Investigator as 'not related' or 'related'. Events other than 'not related' will be considered related in the clinical study report.

Not related: The event is most likely produced by other factors such as the subject's clinical condition, intercurrent illness, or concomitant medications or procedures and does not follow a known response pattern to the study device, or the temporal relationship of the event to study device administration makes a causal relationship unlikely.

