Related: This relationship suggests that a reasonable temporal sequence of the event with device administration exists and, based upon known or previously reported adverse reactions to the device or class of devices or judgment based on the Investigator's clinical experience, the association of the event with the study device seems likely.

The severity (intensity) of AE will be graded according to the following definitions:

Mild: The subject experiences awareness of symptoms but these are easily tolerated or managed without specific treatment.

Moderate: The subject experiences enough discomfort to cause interference with usual activity, and/or the condition requires specific treatment.

Severe: The subject is incapacitated with inability to work or do usual activity and/or the event requires significant treatment measures.

An unexpected AE is one that is not consistent with the subject's past medical or acute burn history and is not evident from previous clinical experience with the test product or reasonably anticipated from pre-clinical information. An AE will be classified as 'serious' when it refers to any event during the 12-month study period that results in any of the following:

- Death
- Life-threatening adverse experience (i.e., the subject was at immediate risk of death from the reaction as it occurred)

- Inpatient hospitalization or prolongation of existing hospitalization
- Persistent or significant disability or incapacity
- A medically significant event or one requiring intervention to prevent one of the outcomes listed above and suspected to be due to the test product

All SAE will be followed until stabilization or improvement.

Clinical site personnel will be trained to follow study processes for reporting SAE. SAE reports will be managed by the clinical research team. The Principal Investigator will manage the process of ensuring that reports are completed appropriately and forwarded in a timely manner to all required recipients. The Principal Investigator will also assess individual and accumulating SAEs, AEs, and other safety data on a regular basis to identify any safety signals that should be brought to the attention of the Sponsor, , IRB offices, and/or the FDA.

Reporting for SAE which **are expected and not related** to KeraStat Gel will be as follows:

- The Principal Investigator (PI) will be notified within 24 hours of the Investigator becoming aware of any SAE that is expected or not related to the test product.

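### Adverse-event causality is rated against KeraStat Gel but not against Mepilex Ag, so related-AE counts, and SAE counts resting on suspicion of the test product, are not comparable between the two burns

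*Combined protocol and SAP*

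**What the plan says.** The Design section describes a within-subject trial in which KeraStat Gel and Mepilex Ag are each randomised to one of two burns. The provisions on AE causality are in the section on reporting of unanticipated problems, adverse events or deviations:

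- **Rating rule.** "The relationship between the application of KeraStat Gel and the AE will be determined by the Investigator", on a two-level scale (related or not related). Anything not rated as unrelated is to be treated as related in the clinical study report.
- **CRF items.** "The time of the onset, location, duration, intensity, relationship to the test product, treatment, and follow-up will also be captured on the CRF".
- **Definition of related.** Among other conditions, "the association of the event with the study device seems likely". The device is in the singular.
- **A second statement of scope.** Earlier in the same section, AEs are to be "evaluated for relationship to KeraStat Gel or dressing-related procedures".
- **AE definition.** Events are those "associated temporally with the use of the test product, whether or not considered related to the test product".
- **Seriousness.** The last criterion in the SAE list, on medically significant events or those needing intervention, includes a condition that the event is suspected to be due to the test product.

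Under Risks and Benefits, the known risks include "an allergic reaction to the dressings, sedatives, narcotics, or any other drugs". The Analytical Plan gives one comparative safety summary: "The incidence of adverse events will be reported and summarized by treatment group", with MedDRA coding.

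**The concern.** A one-sided causality question is ordinary in a single-product study. Here the comparator is also randomised, on the same person, and AEs are to be summarised by dressing. A reaction judged to be caused by Mepilex Ag has no field in which that judgement can be recorded, and under the rating rule taken alone it would be entered as not related. The same reaction at the other burn would be entered as related.

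The protocol commits relatedness to the clinical study report, so some display of related events is intended. If that display is split by dressing, or read that way, the two columns would not measure the same thing. The judgement is also made when the event occurs, in an open-label study, and reconstructing it later for the Mepilex Ag burn would be weak.

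**Working it through.** No arithmetic applies. The documents give no AE rate, no safety margin and no hypothesis test on AEs, so there is no figure to reproduce. The check is a comparison of the provisions.

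1. **Is there any rating against Mepilex Ag?** The rating rule names KeraStat Gel. The CRF item names the test product. The definitions of related and not related refer to the study device. The definition of an unexpected AE refers to the test product, and the SAE reporting routes refer to KeraStat Gel or the test product. Risks and Benefits uses the term study dressings for KeraStat Gel and its secondary dressings. No provision asks for causality with respect to Mepilex Ag.

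2. **Does the wider scope statement supply one?** It adds dressing-related procedures and does not confine them to the KeraStat burn. An event caused by a dressing procedure on the Mepilex Ag burn could therefore be rated as related. The statement still falls short in four ways: it names procedures and not the Mepilex Ag product; the listed CRF items carry no matching field; the definition of not related names concomitant procedures among the alternative causes, which pulls the other way; and one pooled rating would not show which dressing was blamed. The two scope statements are inconsistent.

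3. **Which planned outputs use the rating?**
   - All-AE incidence by treatment group does not. An AE placed at the Mepilex Ag burn counts there whatever its causality label.
   - Related-AE reporting in the clinical study report does. No table by dressing is specified, but the SAP with mock tables is still to be finalised before database lock.
   - SAE classification does in part. A medically significant reaction to Mepilex Ag that meets no other criterion would not be serious if the suspicion condition governs the whole item, while the same reaction to KeraStat Gel would be. If the condition governs only the clause on intervention, the asymmetry is confined to that clause. The wording allows both readings.

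4. **Does recorded location replace a second rating?** Location lets a wound-site event be assigned to Burn A or Burn B. It does not separate a dressing reaction from the ordinary course of the burn, which is what the causality rating is for.

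**The case against.** The strongest reply is that the plan never proposes the comparison that would be distorted. The only by-treatment safety summary is all-AE incidence, and relatedness plays no part in it. That is correct. Three stronger readings are tempting, and the documents do not support them:

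- **That the by-treatment safety comparison is one-sided, or wrong in a known direction.** The planned comparison counts all AEs and does not use the rating.
- **That the Mepilex Ag burn can have no related events by construction.** The wider scope statement leaves room for an event from a dressing procedure on that burn to be rated as related. Zero is not guaranteed.
- **That reactions to the control dressing are hidden.** AEs are defined regardless of relationship and recorded with location, and the Design section has AE recording completed for each burned area on days 14 and 28. Such a reaction lacks a causality label, not a record. The Investigator's discretion over AEs not requiring intervention is a separate matter and is not specific to either dressing.

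One could also assume a reaction rate and test the resulting related-AE counts. The documents give no such rate and plan no such test, so the result would say nothing about this trial.

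It can further be said that Mepilex Ag is the institutional standard of care and that the SAP can still settle how related events are displayed. The second point helps only in part: a SAP can decide what to tabulate, but it cannot supply a judgement that the CRF did not collect.

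**Conclusion.** The point holds in a limited form. The protocol specifies a causality rating for KeraStat Gel and none for the randomised comparator; its two statements of scope differ; and one SAE criterion depends at least in part on suspicion of the test product. Related-AE counts, and SAE counts resting on that criterion, would therefore not be comparable between the two burns. All-AE incidence by treatment group, the primary outcome and the efficacy analyses are unaffected.

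The size cannot be expressed as a number, because no reaction rate is given for either dressing. The consequence arises only if related-AE or SAE counts are read by dressing. The plan does not specify such a table, but it is foreseeable, since relatedness goes into the study report and AEs are summarised by treatment group. This is an inexpensive improvement worth making, not a flaw that undermines the trial. The conclusion assumes that the CRF collects what the protocol lists and nothing more on causality.

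**What to change.** 1. Replace the single rating with two, using the same definitions: related or not related to KeraStat Gel or its dressing procedure; related or not related to Mepilex Ag or its dressing procedure.
2. Record the burn affected as A, B or neither. Location already gives most of this for wound-site events; an explicit code makes it analysable and gives systemic events a category of their own.
3. Reconcile the passages: the rating rule, the wider scope statement, the definitions of related and not related, and the SAE criterion that refers to the test product. State to which part of that criterion the suspicion condition applies.
4. In the SAP, summarise related burn-site AEs from both ratings.

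If the second rating is not added, the protocol and SAP should say that related-AE and SAE counts will not be compared between burns.

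The cost is about one extra CRF field per AE, a burn code that largely duplicates location, and a few sentences of text. No visit, procedure or sample-size change is needed.
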